7.3. Audits/ Inspections

In addition to the monitoring activities, audits can be conducted by the sponsor or assigned auditors. These audits may include checking the whole course of the study, documentation, trial centre, investigators and the monitor.

The competent regulatory authorities may also conduct inspections.

With his/her participation in the study, the investigator agrees to support the activities of the auditor/inspector, provide her/him with direct access to the source documents, study documentation and give her/him the opportunity to audit/inspect the study site, laboratory facilities, storage of the investigational product, etc.

7.4. Documentation: Collection, Handling, Storage and Archiving of Data

7.4.1. Case Report Form

The trial Case Report Form (CRF) is the primary data collection instrument for the trial. All data requested on the CRF must be recorded. All missing data must be explained.

For this project, electronic Case Report Forms (eCRFs) will be used. The Clinical Data Management System [secuTrial "SecuTrial"] will be used for data capture, processing and storage of study data. Data entry is performed at the investigational site by clinical staff after having received training and a user manual for the electronic CRF. Training and the user manual will detail procedures to be followed in case of technical problems. Queries resulting from edit checks and/or data verification procedures will be posted electronically in the eCRF.

Protocol		
Protocol code and Short Title:	P-pVAC-SARS-CoV-2	Date/Version:08.03.2021/V1.4

The Clinical Trial Data Management System (CDMS) is validated and changes are tracked via an audit trail.

The correctness of entries in eCRFs will be confirmed by dated signature of an authorized investigator. The Principal investigator is responsible for ensuring that all sections of the eCRF are completed correctly and that entries can be verified against source data. The Principal investigator has to verify the eCRFs via dated electronic signature after completion of the eCRF.

7.4.2. *Source Data*

Source data is all information, original records of clinical findings, observations or other activities in a clinical trial necessary for the reconstruction and evaluation of the trial. Source data are contained in source documents. Examples of these original documents and data records include: hospital records, clinical and office charts, laboratory notes, memoranda, volunteers' diaries or evaluation checklists, pharmacy dispensing records, recorded data from automated instruments, copies or transcriptions certified after verification as being accurate and complete, x-rays, CTs, MRIs, ultrasound reports, volunteer files, and records kept at the pharmacy, at the laboratories, and at medico-technical departments involved in the clinical trial.

7.4.3. *Data Handling*

Authorized clinical staff at the investigational site will enter the data into the eCRF using an access controlled, audit-trailed, ICH/GCP compliant, validated system. Entered data will be subjected to plausibility checks directly implemented in the eCRF, monitoring and medical review. Implausible or missing data will be queried. Database lock will be performed after completion of data entry, data cleaning and a final data review.

7.4.4. *Preparation/Handling/Storage/Accountability of biological samples*

Biological samples collected under this protocol may be used in accordance with the study informed consent form to conduct protocol related safety and immunogenicity evaluations, exploratory laboratory evaluations related to the SARS-CoV-2 infection the vaccine was designed to prevent, exploratory laboratory evaluations related to vaccine research in general and for research assay validation. All biological samples obtained within the study will be identified solely by means of the individual identification code (Patient ID). Samples will be

Protocol		
Protocol code and Short Title:	P-pVAC-SARS-CoV-2	Date/Version:08.03.2021/V1.4

either processed directly or for PBMC and serum samples for immunogenicity analysis stored until further analyses. Storage of biological samples on a computer will be done in accordance with local data protection law and will be handled in strictest confidence. For protection of these data, organizational procedures are implemented to prevent distribution of data to unauthorized persons. The appropriate regulations of local data legislation will be fulfilled in its entirety. Samples are stored at the Department of Immunology, Tuebingen. Only investigators or their designees will have access to the samples and corresponding data. Sample tracking and preparation will be performed according to established standard operating procedures. The biological samples will be destroyed at the latest 30 years after the end of the study. If a study subject withdraws consent to participate in the study all samples taken and identifiable are destroyed without prior analysis if requested.

7.4.5. *Handling of missing data and drop outs*

Missing values will be predicted based on plausible assumptions that account for the uncertainty due to missing data. For patients with unknown status for the primary endpoint, i.e. a volunteer without complete follow-up and without any SAE until the last known study site contact, a detailed report on the course should be presented by the investigator and discussed concerning probable unknown SAEs and the reasons for drop-out. If substantial reason will be found that the person could have experienced a SAE, this will be interpreted as failure and the recruitment should be stopped accordingly. Otherwise the safety of the person will be interpreted as success, i.e. the subject will be interpreted to have not experienced a SAE. If this decision cannot be precisely concluded, patient will be considered as drop-out. All missing data or inconsistencies will be resolved by the responsible investigator.

7.4.6. *Storage and Archiving of Data*

According to the EU Clinical Trial Regulation 536/2014 all essential trial documents (e.g. CRF) will be archived for at least 25 years after the trial termination. The investigator(s) will archive all trial data (source data and Investigator Site File (ISF) including subject identification list and relevant correspondence) according to the Guideline ICH GCP (E6) and to local law or regulations.

8. Statistical Analyses

8.1. Study Population Definition

8.1.1. *Sample Size and Power Consideration*

In this phase I study the safety/toxicity of one vaccination will be investigated. For this purpose, it will be investigated whether the incidence of severe adverse events (SAE) associated with administration of CoVac-1 exceeds a predetermined rate of 5% (= P1 = alternative hypothesis) in the whole study population. Safety of the CoVac-1 vaccine is shown if no SAE (= P0 = null hypothesis) occurs in the study population. An evaluable sample size of 33 achieves 81.6% power to detect a difference (P1-P0) of 0.0499 using a one-sided exact test based on the binomial distribution with a target significance level of 0.05. The actual significance level achieved by this test is 0.003. These results assume that the population proportion under the null hypotheses (P0) is 0.0001. Assuming a dropout rate of 7.5% (percentage of subjects that are expected to be lost at random during the course of the study and for whom no response data concerning existence of SAE will be collected, i.e. will be treated as “missing”) the total number of 36 subjects should be enrolled in the study in order to end up with 33 evaluable subjects. Sample size computed using PASS 2020 (NCSS, LLC, Kaysville, Utah, USA).

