To avoid bias in treatment, a manualized process protocol as well as monitoring and treatment reports are implemented. The volunteer selection will be documented. Reasons for refusal will be assessed. To avoid bias in data analysis, monitoring and analysis by intention-to-treat are planned. Data analysis will be conducted by an independent statistician.

Figure 1: Overall Study Design

Protocol		
Protocol code and Short Title:	P-pVAC-SARS-CoV-2	Date/Version:08.03.2021/V1.4

Figure 2: Individual Study Procedure

[figure not shown]

Figure 3: Treatment sequence

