8.2. Analysis Primary Variables

The occurrence of critical events (SAE) associated with administration of CoVac-1 should be reported to the Sponsor (section 9.3.1) and documented immediately in the eCRF (within 48h). The statistical center will evaluate the occurrence of critical events using automatized alerts of the e(CRF) on a daily basis and distribute this information to the Sponsor/DSMB. If one critical event will be observed, the formal statistical stopping rule of the study is reached and no further recruitment is adequate. Otherwise the safety of the procedure will be accepted, if no out of 33 volunteers will experience a critical event.

No further statistical tests with confirmatory aim are planned.

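### Observing no related SAE does not show safety against the plan's 5% benchmark: 0/33 excludes only rates above 8.7% and 0/36 only rates above 8.0% (one-sided 95%)

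*Supplement*

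**What the plan says.** Section 8.1.1 of protocol V1.4, repeated in the synopsis, asks whether the incidence of SAEs associated with CoVac-1 "exceeds a predetermined rate of 5% (= P1 = alternative hypothesis) in the whole study population". The null value is fixed by assuming that "the population proportion under the null hypotheses (P0) is 0.0001". The design is evaluated "using a one-sided exact test based on the binomial distribution with a target significance level of 0.05", and the text adds: "The actual significance level achieved by this test is 0.003". On power it states: "An evaluable sample size of 33 achieves 81.6% power to detect a difference (P1-P0) of 0.0499". With 7.5% drop-out allowed for, 36 are enrolled.

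The conclusion to be drawn is "Safety of the CoVac-1 vaccine is shown if no SAE (= P0 = null hypothesis) occurs in the study population".

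Section 8.2 first says that one critical event reaches the formal stopping rule, then continues: "Otherwise the safety of the procedure will be accepted, if no out of 33 volunteers will experience a critical event". It adds that no other confirmatory test is planned. Section 8.6 triggers on the first related SAE in the study population, and section 6.8 lists the same event as the statistical stopping rule. Section 3 says that "analysis by intention-to-treat are planned".

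**The concern.** The hypotheses are arranged so that safe is the null and a 5% rate is the alternative. Safety is then concluded by not rejecting the null. The strictly controlled error (0.003) is that of condemning an essentially harmless vaccine. The error that matters for a safety claim, accepting a vaccine whose related-SAE rate is 5%, is the type II error, and it is far larger.

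This is the only confirmatory conclusion in the trial. Section 1.1.4 says the trial was conceived to prove safety and immunogenicity. Section 1.2.1 says that confirming safety will allow the approach to be carried over to infected patients. A report could state that safety was shown, in line with the protocol, when the best possible result is still compatible with rates above the benchmark the protocol chose.

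**Working it through.** **Inputs (section 8.1.1):** P0 = 0.0001; P1 = 0.05; one-sided target level 0.05; 33 evaluable; drop-out 7.5%. The decision rule is that one or more related SAEs rejects P0 and none accepts safety.

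**1. The plan's own figures**
- Actual significance level: 1 − 0.9999^33 = 0.0033 (stated 0.003).
- Power: 1 − 0.95^33 = 0.8160 (stated 81.6%).
- Enrolment: 33/0.925 = 35.7, rounded up to 36 (stated 36).

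All three reproduce. The sample-size arithmetic is correct.

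**2. Chance of accepting safety when the true rate is 5%**
- n = 33: 0.95^33 = 0.184.
- n = 36: 0.95^36 = 0.158.

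The 18.4% is simply one minus the stated power.

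**3. What zero events excludes.** The exact (Clopper-Pearson) upper limit for 0/n is 1 − 0.05^(1/n) one-sided 95%, and 1 − 0.025^(1/n) two-sided 95%.

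| Result | One-sided 95% upper limit | Two-sided 95% upper limit |
|---|---|---|
| 0/33 | 8.68% | 10.58% |
| 0/36 | 7.98% | 9.74% |
| 0/24 (Part II) | 11.73% | 14.25% |
| 0/12 (Part I) | 22.09% | 26.46% |

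The one-sided limit matches the plan's one-sided 0.05 and is the more lenient of the two. Even with all 36 evaluable, it lies above 5%.

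**4. Number needed to exclude 5% with zero events.** The smallest n with 0.95^n ≤ 0.05 is 59: 0.95^58 = 0.0510 and 0.95^59 = 0.0485. Two-sided, it is 72.

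**5. Denominator.** Sections 8.1.1 and 8.6 refer to the study population. Section 8.2 fixes 33, which section 8.1.1 explains is the number expected to remain evaluable out of 36. Section 8.2 does not say how the statement reads when a different number is evaluable.

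**The case against.** The strongest reply is that the plan never claims to exclude 5% with 95% confidence. It describes a detection design: if the true rate were 5%, at least one related SAE would be seen with probability 81.6%. The 0.05 belongs to the null, and the 18.4% can be read off the printed power. That is a fair account of the calculation, and nothing in the calculation needs changing. It does not rescue the conclusion. A design that misses a 5% rate about one time in five supports a statement of what was and was not excluded. It does not support saying that safety is shown.

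Oversight also does not rest on this sentence. Holding rules, DSMB review, AESI reporting and descriptive CTCAE frequencies all operate independently. That limits the consequences for volunteers, but not for what the report may claim.

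No separate analysis plan is among the documents. Interval methods are often left to one, so the absence of a planned confidence limit is not itself counted here as a fault. Results by part are exploratory (section 8.4), and section 1.2.1 hypothesises similar related-event risk across age groups. The wider limits for Parts I and II are therefore context, not a failed test.

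A reader might go further and infer two things from the 33 in section 8.2, and neither is supported:
- **That the rule covers only 33 of the 36 vaccinated, contrary to intention-to-treat.** Sections 8.1.1 and 8.6 apply to the study population. In section 8.2, acceptance is the alternative to a critical event having been observed, so a related SAE in any volunteer blocks it. The 33 is an expected count, not a chosen subset.
- **That the rule becomes undefined after a fourth drop-out.** Section 7.4.5 reviews each incomplete follow-up and classes it as failure or success. Only undecidable cases become drop-outs, and the rule in section 8.1.1 has meaning at any number evaluable.

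**Conclusion.** The point holds for the inference and not for the arithmetic. With no related SAE, the trial excludes rates above 8.7% (33 evaluable) or 8.0% (36 evaluable) at one-sided 95% confidence, and does not exclude 5%. A vaccine with a true 5% rate would pass with probability 18.4% (n = 33) or 15.8% (n = 36). These figures assume independent volunteers with a common event rate and complete ascertainment of related SAEs among those counted. They take the plan's own one-sided 0.05 as the standard; a two-sided 95% limit would be less favourable (10.6% for 0/33).

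The 33 in section 8.2 is loose wording to be aligned with sections 8.1.1 and 8.6. It does not restrict whom the rule covers.

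**What to change.** Keep 36 volunteers, the sample-size calculation and the stopping rule as they are. In the synopsis and sections 8.1.1 and 8.2, replace the statements that safety is shown or accepted with:

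> With no related SAE among n evaluable volunteers, the trial excludes a related-SAE rate above the one-sided 95% exact upper limit (8.7% for n = 33, 8.0% for n = 36). The probability of observing none at a true 5% rate is 18.4% for n = 33 (15.8% for n = 36).

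Report the exact limit for the number actually evaluable, and give Parts I and II descriptively (22.1% for 0/12, 11.7% for 0/24). In section 8.2, replace the fixed 33 with the study population, as in sections 8.1.1 and 8.6.

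The cost is an amendment of wording and three exact limits in the report. No volunteers or procedures are added. The stated conclusion becomes less favourable.

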8.2. Analysis Primary Variables

The occurrence of critical events (SAE) associated with administration of CoVac-1 should be reported to the Sponsor (section 9.3.1) and documented immediately in the eCRF (within 48h). The statistical center will evaluate the occurrence of critical events using automatized alerts of the e(CRF) on a daily basis and distribute this information to the Sponsor/DSMB. If one critical event will be observed, the formal statistical stopping rule of the study is reached and no further recruitment is adequate. Otherwise the safety of the procedure will be accepted, if no out of 33 volunteers will experience a critical event.

No further statistical tests with confirmatory aim are planned.

8.3. Analysis Secondary Variables

Safety

The statistical analysis of the secondary endpoint will be done in a descriptive manner. No statistical tests with confirmatory aim are planned. The toxicity and safety will be described by absolute and relative frequencies using CTCAE V5.0-scoring.

Protocol		
Protocol code and Short Title:	P-pVAC-SARS-CoV-2	Date/Version:08.03.2021/V1.4

Efficacy

The rate of patients with induction of peptide-specific T-cell responses within a maximum of 56 days after vaccination will be the secondary endpoint for efficacy. T-cell responses will be assessed as described in section 6.3.1

The rate of patients with induction of antibody responses within a maximum of 56 days after vaccination will be the secondary endpoint for efficacy. The antibody response will be assessed as described in section 6.3.1

8.4. Subgroup Analysis

Exploratory subgroup analyses are planned for each part (I and II) regarding primary and secondary endpoints.

8.5. Interim Analysis

The primary endpoint will be evaluated in a sequential manner after every consecutive included volunteer has reached day 28. No further formal interim efficacy analysis will be performed during the conduct of the study.

8.6. Stopping Rules

The pre-defined stopping rule for the study is reached if one critical event (SAE as defined in section 9.1.5) associated with administration of CoVac-1 will be observed in the study population resp. if the first critical event will be observed.

The sponsor has the right to terminate the trial prematurely if there are any relevant medical or ethical concerns, or for reasonable administrative reasons. If such action is taken, the reasons for terminating the trial have to be documented in detail. All volunteers who are not considered end of study must undergo a final examination, which must be documented.

Criteria for termination of the study as a whole are:

- An unacceptable profile or incidence rate of adverse events/ adverse events of special interest revealed in this or any other study in which at least one of the investigational products of this trial is administered.
- Significant number of cases of death associated with the study treatment.

Protocol		
Protocol code and Short Title:	P-pVAC-SARS-CoV-2	Date/Version:08.03.2021/V1.4

- Any other factor that in the view of the sponsor constitutes an adequate reason for terminating the study as a whole.

The Sponsor has to be informed without delay if any investigator has ethical concerns.

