2.3.1. Exploratory Endpoints

- Characteristics of T-cell response on Visits 2, 3, 4, 5 measured by ELISpot/ICS. This includes:
 - Phenotyping of SARS-CoV-2 specific T-cells (CD4, CD8 etc.) by flow cytometry
 - Characterization of cytokine profiles of SARS-CoV-2 specific T cells (TNF, IFN, IL-2, CD107a etc.) by intracellular cytokine staining
 - Recognition rate defined as percentage of peptides inducing a T cell response in one individual
 - Intensity of T cell response to a single SARS-CoV-2 T cell epitope included in the CoVac-1 vaccine
- Induction of long-term SARS-CoV-2 specific T-cell responses 3 and 6 months after peptide vaccination.
- Induction of antibodies specific to the SARS-CoV-2 T-cell epitopes included in the CoVac-1 vaccine measured by ELISA. In case of unexpected detection of CoVac-1 specific antibodies the following assays will be performed:
 - Individual neutralization antibody titers
 - Seroconversion rates
 - Calculation of geometric mean titers (GMT) for neutralizing and binding antibodies
- Biomarkers and clinical characteristics influencing immunogenicity.

Protocol		
Protocol code and Short Title:	P-pVAC-SARS-CoV-2	Date/Version:08.03.2021/V1.4

3. Study Design

This is an interventional, open-label, phase I trial evaluating the CoVac-1 vaccine, a single dose SARS-CoV-2 specific multi-peptide vaccine combined with the TLR1/2 ligand XS15 emulsified in Montanide ISA 51 VG in adults. The study is divided into two parts, which will recruit consecutively. Prior to initiation of the next part, the previous part must have completed recruiting, and day 28 of the last patient enrolled must have passed. After interim safety analysis and approval from the authorities (section 9.5), the next study part starts recruiting (Figure 1 and 2).

The first volunteer included in the trial will be hospitalized after vaccination and closely monitored. This patient is observed until day 28 and possibly arising safety issues are reported to and decided on by the Sponsor. Thereafter, no more than one subject per day will be treated/vaccinated. 28 days following vaccination of the 12th volunteer, there will be an interim analysis of safety and a safety review by the data safety monitoring board (DSMB) as well as a substantial amendment to the regulatory authorities (PEI and EC) before proceeding to Part II. Part II must not start recruiting prior to approval by authorities. Volunteers of part II are treated simultaneously. Details can be found in figure 3.

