6.5. Vaccination holding rules

Safety holding rules for each subject will apply throughout the study period until interim safety analysis (V4). Vaccination of further study subjects in the consecutive study phase will not occur until a safety review has been conducted by the DSMB and only by approval a holding rule can be resolved. If a holding rule is activated, the PI will inform the Sponsor within 48 hours. The Sponsor will inform the responsible authorities (PEI and EC).

If the DSMB permits the resumption of injections, a formal request with pertinent data must be submitted to ECs and PEI. The discontinuation of a holding rule should be communicated to all entities in the same manner and timeframe as described above.

The DSMB safety review will consider:

- The relationship of the AE or SAE to the vaccine or other possible causes of the event.
- If appropriate, additional screening or laboratory testing for other volunteers to identify those who may develop similar symptoms and alterations to the current informed consent form will be discussed.

All injected volunteers will be followed for safety until resolution or stabilization (if determined to be chronic sequelae) of their AE.

The holding rules are as follow:

Protocol		
Protocol code and Short Title:	P-pVAC-SARS-CoV-2	Date/Version:08.03.2021/V1.4

- **Solicited local ADRs:** If more than 30% of injections are followed by Grade ≥ 3 solicited swelling or pain or Grade 4 redness (first occurrence at any time after vaccination) and persisting at Grade 3 (swelling or pain)/4 (redness) for > 48 h to maximum 72 hours depending upon symptom severity and kinetics.
- **Solicited systemic AEs:** If more than 25% of injections are followed by Grade 3 solicited systemic AE beginning within 3 days after study injection (day of injection and 2 subsequent days) and persisting at Grade ≥ 3 for > 48 h to maximum 72 hours depending upon symptom severity and kinetics.
- **Unsolicited AEs:** If more than 25% of volunteers develop a Grade ≥ 3 unsolicited AE (including laboratory AE and physical observations) that is considered probably or definitely related to injection and persists at Grade 3 for > 48 to maximum 72 hours depending upon symptom severity and kinetics.
- A suspected unexpected serious adverse drug reaction (SUSAR) occurs that is life-threatening or results in death.

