6.8. Premature termination of the trial

The trial may be prematurely terminated, if in the opinion of the sponsor and coordinating investigator, there is sufficient reasonable cause. Written notification documenting the reason for study termination will be provided to the investigators.

In case of the following situations a premature termination of the trial has to be considered:

Protocol		
Protocol code and Short Title:	P-pVAC-SARS-CoV-2	Date/Version:08.03.2021/V1.4

- Observation of one SAE associated with administration of CoVac-1 (Statistical Stopping rule of the study)
- Serious adverse drug reactions / not justifiable toxicity
- Substantial changes in risk-benefit considerations
- New insights from other trials
- Insufficient efficacy
- Insufficient recruitment rate

The DSMB will monitor the study conduct and the safety aspects of the trial on a regular basis, and will give recommendations to the coordinating investigator/ the sponsor whether to stop the trial or to change the trial protocol. The sponsor will then decide on the actions to be taken. According to the German drug law (§42a), the trial may be suspended or prematurely terminated by decision of the competent authority (PEI).

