9.3.2. Assessment of Severity and Causality

The investigator will also provide an assessment of the severity of the event according to CTCAE criteria (Version 5.0) and causal relationship between the event and each of the investigational products or trial procedures.

AEs and SAEs should be evaluated for severity according to the following scale:

- Grade 1 Mild; asymptomatic or mild symptoms; clinical or diagnostic observations only; intervention not indicated.
- Grade 2 Moderate; minimal, local or noninvasive intervention indicated; limiting age-appropriate instrumental Activities of Daily Living (ADL).
- Grade 3 Severe or medically significant but not immediately life-threatening; hospitalization or prolongation of hospitalization indicated; disabling; limiting self care ADL.
- Grade 4 Life-threatening consequences; urgent intervention indicated.
- Grade 5 Death related to AE.

The investigator must determine the causal relationship between the administration of IMP and the occurrence of an AE/SAE as defined below:

Related: There is a reasonable possibility that the SAE may be related to the IMP (e.g. favorable temporal relationship, positive dechallenge: symptoms are receding when IMP is withdrawn or the dose reduced, positive rechallenge: symptoms are reappearing when the IMP is reintroduced or the full dose is re-administered)

Not Related: There is no reasonable possibility that the SAE is related to the IMP (e.g. there is a plausible alternative cause for the SAE that better explains the occurrence of the SAE)

Outcome of AEs

The outcome of an AE at the time of the last observation will be classified as:

Recovered/ resolved	All signs and symptoms of an AE disappeared without any sequels at the time of the last interrogation.
Recovering/ resolving	The intensity of signs and symptoms has been diminishing and/ or their clinical pattern has been changing up to the time of the last interrogation in a way typical for its resolution.
Not recovered/ not resolved	Signs and symptoms of an AE are mostly unchanged at the time of the last interrogation.

Protocol		
Protocol code and Short Title:	P-pVAC-SARS-CoV-2	Date/Version:08.03.2021/V1.4

Recovered/ resolved with sequel	Actual signs and symptoms of an AE disappeared but there are sequels related to the AE.
Fatal	Resulting in death. If there are more than one AE, only the AE leading to death (possibly related) will be characterized as 'fatal'.

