9.4.1. *Reporting to Data and Safety Monitoring Board*

The DSMB will be informed of all safety-relevant events by the Sponsor / CI. An interim safety analysis will be sent to the DSMB after completion of Part I and Part II. The DSMB will decide on trial continuation. Additionally, the DSMB will be informed as soon as a IMP-related SAE/SUSAR occurs or a holding rule is reached. Meetings may be convened as conference calls/Emails as well as in person.

9.4.2. *Report to the Investigator*

The Sponsor / CI will inform investigators of all SUSARs including all relevant further information within the periods set by the authority.

If new information becomes known that is different from the scientific information given to the investigator, all investigators will be informed of this by the sponsor.

9.5. *Interim Safety analysis*

Two or more interim safety analyses will be undertaken to guide decision and whether to start recruitment in the consecutive trial parts. Upon completion of a study part, screening will be interrupted until safety approval of DSMB is available. The data to be evaluated by the DSMB will include (report):

- Solicited and unsolicited AEs/ADRs, AESIs and SAEs
- Review and, if necessary, assessment of (S)AE relatedness to IMP

Protocol		
Protocol code and Short Title:	P-pVAC-SARS-CoV-2	Date/Version:08.03.2021/V1.4

The DSMB decision will be documented in a TMF. The information will be distributed to the study sponsor, the drug manufacturer, all investigators/trial site and the ZKS Department Pharmakovigilanz for information.

The interim safety analysis together with the DSMB decision and first data on immunogenicity of CaVac-1 will be send to the authorities (PEI and ethic committee) as a substantial amendment to gain approval for recruiting in Part II and III of the planned study. After responsible authorities approve the submitted documents, the study will continue enrolment as planned.

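### Protocol V1.4 gives conflicting instructions for the first CoVac-1-associated SAE, and parts of the holding and interim rules do not fit the causality scale or the two-part design

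*Supplement*

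**What the plan says.** All references are to protocol V1.4.

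- **8.6 (with 8.2).** "The pre-defined stopping rule for the study is reached if one critical event (SAE as defined in section 9.1.5) associated with administration of CoVac-1" is observed. Section 8.2 calls this the formal statistical stopping rule and says further recruitment is not appropriate once it is reached. Safety is accepted only if none of 33 volunteers has such an event.
- **6.8.** "In case of the following situations a premature termination of the trial has to be considered". The first item on the list is one CoVac-1-associated SAE, labelled there as the statistical stopping rule. The DSMB recommends and the sponsor decides.
- **9.4.1.** The DSMB decides whether the trial continues.
- **6.5.** Vaccination is held if "A suspected unexpected serious adverse drug reaction (SUSAR) occurs that is life-threatening or results in death". The hold can be lifted with DSMB approval, followed by a request to the ethics committee and the authority. A separate hold applies if more than 25% of volunteers have a persisting Grade 3 or higher unsolicited AE "that is considered probably or definitely related to injection".
- **9.3.2.** Causality has two categories. Related means "There is a reasonable possibility that the SAE may be related to the IMP"; the other category is Not Related.
- **8.6, further criterion.** "Significant number of cases of death associated with the study treatment".
- **Section 3.** "Volunteers of part II are treated simultaneously". Figure 3, to which the text refers for details, is not reproduced in the copy reviewed.
- **8.5.** The primary endpoint is evaluated sequentially, as each consecutive volunteer reaches day 28.
- **9.5.** "Two or more interim safety analyses will be undertaken to guide decision and whether to start recruitment in the consecutive trial parts". The section also refers to approval for recruiting in Parts II and III, although the design now has two parts.

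**The concern.** Part I is complete, so V1.4 governs the vaccination of the 24 Part II volunteers, aged 56 to 80, with or without pre-existing conditions. If one of them has an SAE judged related to the vaccine, site, sponsor and DSMB can each find text supporting a different action: end recruitment (8.2, 8.6), consider termination with the sponsor deciding (6.8), let the DSMB decide (9.4.1), or, for a fatal or life-threatening SUSAR, hold and possibly resume (6.5). A safety rule has to be readable in one way on the day it is needed.

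Two further points bear on whether the rules can be applied as written. The unsolicited-AE hold depends on grades of relatedness that the causality section does not define. And the evaluation described in 8.5, together with the reviews promised in 9.5, does not match a second part whose volunteers are treated simultaneously and which no further part follows.

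**Working it through.** **1. The plan's own figures.** Inputs from 8.1.1: n = 33 evaluable, P0 = 0.0001, P1 = 0.05, one-sided exact binomial, 7.5% dropout. The rule is one or more events in 33, so the probability of reaching it is 1 − (1 − p)^33.

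- p = 0.05: 1 − 0.95^33 = 0.8160 (stated 81.6%).
- p = 0.0001: 1 − 0.9999^33 = 0.0033 (stated 0.003).
- 33 / 0.925 = 35.7, rounded up to 36 (stated 36).

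Stopping at the first event in strict sequence gives Σ p(1 − p)^(k−1) for k = 1 to 33, again 0.8160 and 0.0033. The figures do not depend on the order or pace of dosing.

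**2. The same event, four provisions.**

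| Section | Trigger | Consequence | Who decides |
|---|---|---|---|
| 8.2 / 8.6 | one associated SAE | stopping rule reached, recruitment ends | automatic as worded |
| 6.8 | the same | termination to be considered | sponsor, on DSMB recommendation |
| 9.4.1 | safety report or IMP-related SAE | decision on continuation | DSMB |
| 6.5 | fatal or life-threatening SUSAR | hold that can be lifted | DSMB approval, then request to ethics committee and authority |

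Under 9.3.7 a SUSAR is an SAE with suspected relation to the product. Reading associated in 8.6 as suspected-related, every event that triggers the SUSAR hold has already reached the 8.6 rule. No section says which provision then governs. Likewise, a vaccine-associated death is an SAE under 9.1.5, so the 8.6 criterion on a number of deaths adds nothing if the one-event rule is binding.

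**3. Holding rules.** Section 6.5 asks for probable or definite relation; 9.3.2 offers Related or Not Related; 9.3.7 uses a third wording, based on definite absence of relation. The percentages have a unit (injections or volunteers) but no stated cohort:

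| Threshold | Part I, 12 | Part II, 24 | Whole trial, 36 |
|---|---|---|---|
| more than 25% | 4 | 7 | 10 |
| more than 30% | 4 | 8 | 11 |

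**4. Part II exposure.** The protocol text does not give the batch size, so it is an assumption here, as are the event rates and the condition that each event is known before the next batch. With batches of b among 24, expected vaccinations before dosing stops are Σ b(1 − p)^(bj) for j = 0 to 24/b − 1.

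| Batch size | p = 0.05 | p = 0.10 |
|---|---|---|
| 1 | 14.2 | 9.2 |
| 2 | 14.5 | 9.7 |
| 6 | 16.0 | 11.8 |
| 12 | 18.5 | 15.4 |
| 24 | 24 | 24 |

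If all 24 were dosed before any event was known, expected events at p = 0.05 are 24 × 0.05 = 1.2, and P(two or more) = 1 − 0.95^24 − 24 × 0.05 × 0.95^23 = 0.339. At p = 0.10 the same probability is 0.708.

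Waiting 28 days between volunteers would take 24 × 28 = 672 days, against a planned 12-month trial. Section 8.5 is therefore unlikely to intend that, but it does not say what it does intend for Part II.

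**The case against.** A reader might infer that the 81.6% and 0.003 fail because the rule is advisory in one place or because Part II is not dosed sequentially. The documents do not support that. Both figures belong to the acceptance criterion in 8.2 (no event in 33), which 6.5 and 6.8 leave untouched, and neither depends on dosing order. They would change only if the narrower SUSAR trigger replaced the one-SAE rule, which the text does not say. (For illustration: if half of related SAEs were fatal or life-threatening SUSARs, that trigger would be reached with probability 1 − 0.975^33 = 0.566.)

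A reader might also infer that the rule cannot act during Part II. That too goes beyond the text. Section 8.2 provides daily eCRF alerts, 9.3.1 requires SAE reports within 24 hours, and 9.4.1 has the DSMB informed as soon as a related SAE occurs. These could stop doses not yet given. The text does not define simultaneous treatment; V1.2 used the word for a Part III with two participants per day. Section 8.5 can be read as allowing overlapping dosing.

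A hold and a stop are different instruments, so a narrower trigger in 6.5 is not in itself a contradiction. Ending recruitment (8.2) and terminating the trial (6.8) are also not identical acts. The references in 9.5 to further reviews and a Part III look like remnants of the three-part design, and the Part I review has taken place. The eCRF is not shown, and the DSMB may assess relatedness itself, so it cannot be said that the unsolicited-AE hold is impossible to evaluate.

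All of this stands. What it leaves is the missing precedence, the two decision-makers, the undefined causality grades, the open denominator and the unclear Part II sequence.

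**Conclusion.** The inconsistency is real in the latest version. For one and the same event the protocol states different consequences (8.2/8.6 against 6.8) and different decision-makers (6.8 against 9.4.1). For the gravest subset it adds a hold that can be lifted (6.5), without saying which provision prevails. One holding rule uses causality grades that 9.3.2 does not define. Its threshold could mean 4, 7 or 10 volunteers, depending on an unstated cohort. Section 3 fits poorly with 8.5, and 9.5 has not been brought into line with two parts.

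The sample-size figures are right for the acceptance rule and need no restatement. The numerical consequence concerns exposure only, and it is conditional. At an assumed 5% related-SAE rate, expected Part II vaccinations lie between about 14 and 24, depending on pacing that the text does not give. The 1.2 expected events and 34% chance of two or more apply to the extreme in which all 24 are dosed before any event is known. The textual conflict does not depend on these assumptions.

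**What to change.** - Reconcile 6.5, 6.8, 8.2, 8.6 and 9.4.1 so that one passage states what follows the first CoVac-1-associated SAE, whether that consequence is binding, who decides, and which provision prevails when a hold and the stopping rule are met by the same event. Refer to that passage elsewhere. State what the criterion on number of deaths adds.
- Align section 3, 8.5 and 9.5 with the actual Part II vaccination sequence and the two-part design. Say what simultaneous treatment means, how the evaluation in 8.5 works alongside it, and which reviews can precede a vaccination. Remove the remaining references to a third part, including the three-cohort sentence in 1.1.4.
- Express the relatedness condition in 6.5 in the categories of 9.3.2, and state the cohort over which the 25% and 30% thresholds are counted. Because this can change how wide the trigger is, its content needs agreement by the sponsor and DSMB.

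Which clinical rule applies is for the sponsor and DSMB; this point asks only that the passages agree. The cost is wording in a protocol amendment and, where needed, the DSMB charter. Sample size, power and acceptance criterion stay as they are.
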